7.3 Handling Potential Intercurrent Events for the Primary and Key Secondary Endpoints

For the primary efficacy analysis, subjects who discontinue the trial with an unknown SVR₁₂ status (after applying backward imputation) will be counted as a failure for SVR₁₂.

7.4 Statistical Analyses for Efficacy

Descriptive statistics will be provided, such as the number of observations, mean, and standard deviation for continuous variables and counts and percentages for discrete variables.

The primary and key secondary efficacy analyses will be performed on the ITT and mITT-VF populations, respectively, as defined in Section 7.2. Supportive secondary efficacy analyses will be performed on the ITT population.

Intercurrent events will be analyzed as described in Section 7.3. For the primary efficacy analysis, subjects who do not have an SVR_{12} result after applying backward imputation will be considered a failure for SVR_{12} .

No data will be imputed for any efficacy analyses except for analyses of SVR endpoints (HCV RNA data) and patient reported outcomes (PRO) questionnaires. Hepatitis C virus RNA values will be selected for the analyses of all SVR endpoints based on defined visit windows. A backward imputation method will be used to impute missing responses for SVR analyses. Details of the backward imputation method and the imputation of missing responses on PRO questionnaires will be described in the SAP.

Summary and Analysis of the Primary Endpoint

The primary endpoint is the achievement of SVR₁₂ (defined as HCV RNA < LLOQ 12 weeks after the last actual dose of study drug) for each subject in the ITT population.

For the primary efficacy endpoint analysis, the number and percentage of subjects achieving SVR₁₂ will be calculated for the ITT population along with a 2-sided 95% confidence interval using Wilson's score method. The superiority of 8-week treatment with GLE/PIB in acute HCV infection to the weighted efficacy threshold described in Section 7.8, which is based on the historical ITT SVR₁₂ rate of treatment with GLE/PIB in PWID and non-PWID subjects with chronic HCV infection, will be demonstrated if the lower bound of the 2-sided 95% confidence interval (using Wilson's score method) for the percentage of subjects achieving SVR₁₂ is greater than the weighted efficacy threshold.

In this analysis, subjects who have OTVF, Relapse₁₂, or post-treatment reinfection (defined below), are missing SVR₁₂ status after backward imputation, or have early premature discontinuation leading to virologic failure will count as SVR₁₂ failures. A summary of reasons for SVR₁₂ non-response will be provided.

Details of the analysis will be documented in the SAP.

Summary and Analysis of Secondary Endpoints

Summary and Analysis of Key Secondary Endpoint

The key secondary endpoint is achievement of SVR₁₂ for each subject in the mITT-VF population.

For the key secondary endpoint analysis, the number and percentage of subjects achieving SVR₁₂ will be calculated for the mITT-VF population along with a 2-sided 95% confidence interval using Wilson's score method.

The superiority of 8-week treatment with GLE/PIB in acute HCV infection to the weighted efficacy threshold described in Section 7.8, which is based on the historical mITT-VF SVR₁₂ rate of treatment with GLE/PIB for PWID and non-PWID with chronic HCV infection, will be demonstrated if the lower bound of the 2-sided 95% confidence interval (using Wilson's score method) for the percentage of subjects achieving SVR₁₂ is greater than the efficacy threshold. The key secondary hypothesis will be tested only if the primary efficacy hypothesis is demonstrated according to the fixed-sequence testing procedure described in Section 7.7. Details of the analysis will be documented in the SAP.

Summary and Analysis of Supportive Secondary Endpoints

Supportive secondary endpoints:

- On-treatment virologic failure (defined as confirmed increase of > 1 log10 IU/mL above nadir during treatment, confirmed HCV RNA ≥ 100 IU/mL after HCV RNA < LLOQ during treatment, or HCV RNA ≥ LLOQ at the EOT with at least 6 weeks of treatment) for each subject in the ITT population.
- Post-treatment relapse (Relapse₁₂: defined as confirmed HCV RNA ≥ LLOQ between EOT and 12 weeks after the last dose of study drug [up to and including the SVR₁₂ assessment time point], excluding cases of reinfection) for each subject in the ITT population who completed treatment as planned (defined as study drug duration ≥ 52 days) with HCV RNA < LLOQ at the EOT and with at least 1 post-treatment HCV RNA value.
- 3. Post-treatment reinfection with HCV (defined as confirmed HCV RNA ≥ LLOQ in the PT period along with the PT detection of a different HCV genotype, subtype, or clade compared with baseline) for each subject in the ITT population.

For each secondary endpoint, the number and percentage of subjects in the ITT population meeting the endpoint will be calculated along with a 2-sided 95% confidence interval using Wilson's score method.

Details of the analyses will be documented in the SAP.

Summary and Analysis of Additional Efficacy Endpoints

Analysis of additional efficacy endpoints will be described in the SAP.

Subgroup Analysis for Efficacy

Subgroup analyses on the percentage of subjects achieving SVR_{12} will be performed. For each subgroup, the number and percentage of subjects achieving SVR_{12} will be calculated for the ITT and mITT-VF populations. For subgroups with at least 5 subjects, a 2-sided 95% confidence interval for the percentage will be calculated using Wilson's score method in the ITT and mITT-VF populations. Analysis of SVR_{12} will be provided for the following subgroups:

- HCV genotype and subtype;
- Sex;
- Age;
- Race;

- Body mass index;
- Baseline HCV RNA level;
- Baseline platelet count;
- Baseline serum albumin;
- Baseline ALT;
- Baseline total bilirubin;
- Geographic region;
- Baseline creatinine clearance/estimated glomerular filtration rate;
- History of diabetes;
- Stable opiate substitution status;
- Non-prescribed drug use status;
- Baseline aspartate aminotransferase to platelet ratio index (APRI);
- Baseline FibroTest;
- Baseline Fibrosis-4;
- Baseline ALT/AST ratio;
- Baseline risk behaviors;
- HIV status;
- Estimated acute HCV infection duration;
- Primary versus re-infection status;
- Baseline fibrosis stage;
- Baseline cirrhosis status;
- Study treatment duration;
- Study treatment compliance.

Details of the analyses will be documented in the SAP.

7.5 Statistical Analyses for Safety

The safety endpoints specified in Section 3.1, where AE endpoints will be based on treatment-emergent AEs and laboratory endpoints will be based on values collected during treatment, will be analyzed on the Safety Analysis Set. Treatment-emergent AEs are defined as those with onset during GLE/PIB treatment through 30 days post-dosing. Laboratory values during treatment are those collected during GLE/PIB dosing. Treatment-emergent hepatic decompensation/hepatic failure events will be identified using the AbbVie Product Medical Dictionary for Regulatory Activities (MedDRA) query, including events such as ascites, hepatic encephalopathy, esophageal variceal bleeding, and spontaneous bacterial peritonitis. For each safety endpoint, the number and percentage of subjects meeting the criteria will be calculated.

7.6 Interim Analysis

Not applicable for this study.

7.7 Overall Type I Error Control

In order to control the family-wise Type I error rate, a fixed-sequence testing procedure will be used for the primary and key secondary efficacy analyses of SVR₁₂ as listed below. The fixed-sequence testing procedure will utilize the sequence of the primary analysis followed by the key secondary analysis.

The multiplicity-controlled efficacy analyses will be performed sequentially in the following order:

- Primary: Superiority of the SVR₁₂ rate of 8-week treatment with GLE/PIB for subjects in the ITT population to the efficacy threshold. If superiority is demonstrated, then proceed to the key secondary efficacy analysis. If superiority is not demonstrated in the primary analysis, then stop the testing procedure (i.e., do not perform the key secondary analysis).
- Key Secondary: Superiority of the SVR₁₂ rate of 8-week treatment with GLE/PIB for subjects in the mITT-VF population to the efficacy threshold. If superiority is demonstrated, then declare superiority for both the mITT-VF and ITT populations. If not, then declare that superiority was demonstrated only for the ITT population.

7.8 Sample Size Determination

The threshold for comparison for the primary efficacy estimand will be derived from a weighted average of the ITT SVR₁₂ rates in the PWID and non-PWID chronically infected populations of subjects who received GLE/PIB in Phase 2 and 3 trials. The ITT SVR₁₂ rate among chronically infected HCV PWID (current/recent PWID) is 88.7% and is 97.8% among chronic non-PWID (former/non-PWID) (Mavyret US Prescribing Information 2020, Section 14.9⁴). The threshold for comparison will be calculated by (proportion of PWID in the ITT population of this study × 88.7%) + (proportion of non-PWID in the ITT population of this study × 97.8%) minus a margin of 6%. Therefore, the threshold would be 82.7% if all subjects in the ITT population of this study are PWID, and it would be 91.8% if all subjects in the ITT population of this study are non-PWID. Similarly, the threshold for the comparison of the key secondary estimand will be derived from a weighted average of the mITT-VF SVR12 rates in the PWID and non-PWID chronically infected populations. The mITT-VF SVR₁₂ rate among chronically infected HCV PWID is 98.2% and is 98.8% among chronic non-PWID. The threshold for comparison will be calculated by (proportion of PWID in the mITT-VF population of this study × 98.2%) + (proportion of non-PWID in the mITT-VF population of this study × 98.8%) minus a margin of 6%. It follows that the threshold would be 92.2% if all subjects in the mITT-VF population of this study are PWID, and it would be 92.8% if all subjects in the mITT-VF population of this study are non-PWID.

It is planned to enroll approximately 283 subjects. Assuming all of the subjects in the ITT population of this study are PWID, 283 subjects will provide 80% power to show that an 88.7% SVR₁₂ rate among acutely infected HCV subjects in the ITT population is superior to a threshold of 82.7% based on the historical ITT SVR₁₂ rate among chronically infected HCV subjects, using a 2-sided 95% confidence

interval. Assuming all of the subjects in the ITT population of this study are non-PWID, 283 subjects will provide greater than 95% power to show that a 97.8% SVR₁₂ rate among acutely infected HCV subjects in the ITT population is superior to a threshold of 91.8% based on the historical ITT SVR₁₂ rate among chronically infected HCV subjects, using a 2-sided 95% confidence interval.

Assuming that approximately 10% of the ITT subjects will not be included in the mITT-VF population and that all of the subjects in the mITT-VF population of this study are PWID, a total of 255 subjects will provide greater than 95% power to show that a 98.2% SVR₁₂ rate among acutely infected HCV subjects in the mITT-VF population is superior to a threshold of 92.2% based on the historical mITT-VF SVR₁₂ rate among chronically infected HCV subjects using a 2-sided 95% confidence interval. Assuming all of the subjects in the mITT-VF population of this study are non-PWID, 255 subjects will provide greater than 95% power to show that a 98.8% SVR₁₂ rate among acutely infected HCV subjects in the mITT-VF population of this study are non-PWID, 255 subjects in the mITT-VF population is superior to a threshold of 92.8% based on the historical mITT-VF SVR₁₂ rate among chronically infected HCV subjects, using a 2-sided 95% confidence interval.

Additionally, the proposed sample size of 283 will provide greater than 94% probability to detect any toxicity that has a true incidence rate of at least 1% in subjects with acute HCV infection. Table 1 shows the probability that a given AE or laboratory toxicity would be observed with a sample size of 283 subjects in the Safety Analysis Set.

True Toxicity Rate	Sample Size	Probability of at Least 1 Subject with Toxicity			
0.5%	283	75.8%			
1%	283	94.2%			
2%	283	99.7%			
3%	283	100%			

Table 1. Sample Size Justification Based on Probability of Observing Any Toxicity

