3 OBJECTIVES AND ENDPOINTS

3.1 Objectives, Hypotheses, and Estimands

The objectives of this study are to assess the safety and efficacy of GLE/PIB 8-week treatment in adults and adolescents with confirmed acute HCV infection.

Glecaprevir/pibrentasvir is expected to achieve a high SVR₁₂ rate and an acceptable safety profile in adults and adolescents with acute HCV infection.

Primary

The primary objective of this study is to demonstrate the efficacy of 8-week treatment with GLE/PIB in adults and adolescents with confirmed acute HCV infection by comparing the SVR₁₂ rate from this study to the historical SVR₁₂ rate in subjects with chronic HCV infection who were treated with GLE/PIB. The primary efficacy objective will be assessed based on the ITT population which is defined as all enrolled subjects who received at least 1 dose of study drug.

The primary hypothesis is that 8-week treatment with GLE/PIB for subjects in the ITT population is superior to an efficacy threshold (described in Section 7.8) based on the historical ITT SVR₁₂ rates of treatment with GLE/PIB in subjects with chronic HCV infection.⁴ This will be shown if the lower bound of the 2-sided 95% confidence interval (using Wilson's score method) for the percentage of subjects in the ITT population achieving SVR₁₂ is greater than the efficacy threshold.

The estimand corresponding to the primary efficacy objective is the percentage of acutely infected HCV subjects assigned 8 weeks of GLE/PIB in the ITT population who achieve SVR₁₂. Subjects who discontinue the study with an unknown SVR₁₂ status will be counted as a failure for SVR₁₂.

Key Secondary

The key secondary objective of this study is the same as the primary objective of this study except that the key secondary objective will be assessed in the modified ITT – virologic failure (mITT-VF) population. The mITT-VF population is defined as all enrolled subjects who received at least one dose of study drug, excluding those who did not achieve SVR₁₂ for reasons other than virologic failure (i.e., those with HCV reinfection, those who did not achieve SVR₁₂ due to early premature discontinuation of study drug, and those who were missing HCV RNA data in the SVR₁₂ window after backward imputation).

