4.2 Discussion of Study Design

Choice of Control Group

An integrated analysis of Phase 2 and Phase 3 studies of GLE/PIB in chronically HCV-infected adults and adolescents who were self-reported as current/recent PWID (referred to hereafter as PWID) versus those who were former/non-PWID (referred to hereafter as non-PWID) was performed, and results of the analysis are presented in the US Package Insert.⁴ This analysis will provide the historical efficacy

control for the current trial. The threshold for comparison for the primary efficacy hypothesis will be derived from a weighted average of the ITT SVR12 rates in the PWID and non-PWID chronically infected populations of subjects. In the Phase 2 and Phase 3 studies, the overall SVR₁₂ rate was 88.7% (55/62) in PWID subjects in the ITT population, with a virologic failure rate of 1.6% (1/62); the overall SVR₁₂ rate was 97.8% (4147/4241) in non-PWID subjects in the ITT population, with a virologic failure rate of 1.2% (50/4241). Excluding subjects who failed to achieve SVR₁₂ due to reasons other than virologic failure yields SVR₁₂ rates of 98.2% (55/56) for PWID subjects and 98.8% (4147/4197) for non-PWID subjects, for the mITT-VF population. Given that the acute HCV population is comprised primarily of PWID patients and the SVR₁₂ rates in the PWID subjects with chronic HCV treated with GLE/PIB are high, an active control arm would not provide value in establishing the efficacy of the 8-week GLE/PIB regimen in the acute population. So, the efficacy of GLE/PIB can be established via comparison to a threshold rather than to non-inferiority to an active control. Consequently, the observed SVR₁₂ rates from the chronically infected subjects (ITT and mITT-VF populations) will be used as historical controls to provide comparators for assessment of GLE/PIB in acutely infected subjects. A threshold for each of the primary and key secondary efficacy analyses of the 8-week GLE/PIB regimen in acute HCV to the historical control is determined by subtracting a margin of 6% from the weighted average of the PWID and non-PWID historical SVR₁₂ rates. A margin of 6% is selected to ensure a minimal loss of efficacy of the 8-week GLE/PIB regimen in acute HCV relative to the historical SVR₁₂ rate in subjects with chronic HCV. Details for calculating the efficacy thresholds are provided in Section 7.8.

Appropriateness of Measurements

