## Table 2.Summary of the Estimand Attributes Corresponding to the
Primary Efficacy Endpoint

	Attributes of the Estimand				
Estimand Label	Treatment	Endpoint	Population	Handling of Intercurrent Events	Statistical Summary
Primary	GLE/PIB 8 Weeks	SVR 12	ITT	Subjects who discontinue the study with an unknown SVR 12 status (after applying backward imputation) will be counted as a failure for SVR 12	Number and percentage of subjects who achieve SVR 12 along with a two-sided 95% CI calculated using Wilson's score method 

The superiority of 8-week treatment with GLE/PIB in acute HCV infection to the weighted efficacy threshold described in Section 2.5, which is based on the historical ITT SVR12 rate of treatment with GLE/PIB in PWID and non-PWID subjects with chronic HCV infection, will be demonstrated if the lower bound of the two-sided 95% CI for the percentage of subjects achieving SVR12 is greater than the weighted efficacy threshold. For the calculation of the efficacy threshold, the proportions of PWID and non-PWID subjects in this study will be determined using PWID Status Classification 1 described in Section 7.1.

The number and percentage of subjects with each reason for  $SVR_{12}$  non-response will be provided. A listing of subjects who do not achieve  $SVR_{12}$  by reason for non-response will also be provided.

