### 9.3.3 Supplementary Analyses of Primary Efficacy Endpoint

As a supplementary analysis of the primary endpoint (Supplementary Analysis 1), the number and percentage of subjects in the ITT population who achieve SVR12 along with a two-sided 95% CI calculated using Wilson's score method will be compared to the

efficacy threshold as calculated using the proportions of PWID and non-PWID subjects in this study and the PWID Status Classifications 2 and 3 as described in Section 7.1.

As a supplementary analysis of the primary endpoint (Supplementary Analysis 2), the number and percentage of subjects in the ITT population with baseline HCV RNA  $\geq$  LLOQ who achieve SVR12 along with a two-sided 95% CI calculated using Wilson's score method will be compared to the efficacy threshold as calculated using the proportions of PWID and non-PWID subjects included in this analysis and the PWID Status Classifications 1, 2, and 3 as described in Section 7.1. Additionally, the number and percentage of subjects with each reason for SVR12 non-response will be provided as well as a listing of subjects who do not achieve SVR12 by reason for non-response.

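### Does the primary analysis need an interval for the 62-subject PWID control behind its threshold?

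*Protocol*

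**What the plan says.** The primary objective (Protocol 3.1, SAP 2.1) is to compare SVR12 in this study with the historical "rate in subjects with chronic HCV infection who were treated with GLE/PIB". The hypothesis in the same section makes this operational: treatment "for subjects in the ITT population is superior to an efficacy threshold (described in Section 7.8"), shown if the lower limit of the two-sided 95% Wilson interval exceeds that threshold.

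Protocol 4.2 says efficacy can be established "via comparison to a threshold rather than to non-inferiority to an active control". It gives the source data: the SVR12 "rate was 88.7% (55/62) in PWID subjects in the ITT population", and 97.8% (4147/4241) in non-PWID subjects. On the margin it says: "A margin of 6% is selected to ensure a minimal loss of efficacy of the 8-week GLE/PIB regimen in acute HCV" relative to the historical rate.

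Protocol 7.8 gives the formula: "The threshold for comparison will be calculated by (proportion of PWID in the ITT population of this study" × 88.7%), plus the matching non-PWID term, minus the margin. Protocol 7.8 and SAP 2.5 enter 88.7% and 97.8% as constants, weight them by this study's PWID mix and subtract 6 points. The threshold therefore lies between 82.7% (all PWID) and 91.8% (no PWID). Under SAP 9.3.2 the mix "will be determined using PWID Status Classification 1".

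The supplementary analyses in SAP 9.3.3 repeat the comparison with the "efficacy threshold as calculated using the proportions of PWID and non-PWID subjects" under the other PWID classifications, and in subjects with quantifiable baseline HCV RNA. The historical rates stay fixed throughout. SAP 9.6 presents SVR12 by PWID status in the ITT and mITT-VF populations, with Wilson intervals for subgroups of at least 5 subjects, and reasons for non-response by PWID status.

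**The concern.** The objective and the margin rationale are worded as a comparison with chronic HCV, but the PWID half of that comparator rests on 62 subjects. Its 95% interval is about 16 points wide, against a 6-point margin. Protocol 4.2 expects acute HCV patients to be mainly PWID, so this small group could carry most of the weight, although no expected share is given.

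The test treats 88.7% as known. If the true chronic PWID rate were higher, a result above the threshold could coexist with a loss of more than 6 points against that true rate. A reader who takes a pass as proof of less than a 6-point loss would then be misled, and no planned table would warn of it.

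**Working it through.** **Inputs.** n = 283, margin 6 points, historical counts 55/62 and 4147/4241 (Protocol 4.2 and 7.8, SAP 2.4 and 2.5); two-sided 95% Wilson interval (Protocol 7.4), z = 1.96.

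**1. Does the test perform as stated?** Wilson lower limit = [p + z²/2n − z√(p(1−p)/n + z²/4n²)] / (1 + z²/n). With all subjects PWID the threshold is 88.7% − 6% = 82.7%.

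- 246/283 = 86.9%: lower limit 86.43% − 3.93% = 82.50%, fails.
- 247/283 = 87.3%: lower limit 86.78% − 3.89% = 82.89%, passes.

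The pass mark is therefore 247. Exact binomial results:

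- Level: P(X ≥ 247 | 0.827) = 2.2%.
- Power: P(X ≥ 247 | 0.887) = 80.4%, against the stated 80%.

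With no PWID the pass mark is 269/283, with level 2.4% and power 99.8% (stated: above 95%). For the hypothesis as defined, the one-sided level is below 2.5% in both cases and the stated power reproduces.

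**2. How uncertain is the control?** Wilson 95% limits are 78.5% to 94.4% for 55/62 and 97.3% to 98.2% for 4147/4241. Only the PWID component is imprecise.

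**3. What would a difference interval show?** With all PWID, the hybrid-score lower limit is d − √[(p − L)² + (U_H − H)²], where p and L are the study rate and its lower limit, H and U_H are the historical rate and its upper limit, and d = p − H.

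- At 247/283: d = −1.4 points; −1.4 − √(4.39² + 5.71²) = −1.4 − 7.2 = −8.6.
- At 253/283: lower limit −6.4.
- At 254/283: lower limit −5.98.

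The interval excludes −6 only from 254 responders. For PWID shares below 100%, the historical limits combine the two groups by adding the squared weighted distances to their Wilson limits.

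| PWID share | Pass mark | Count excluding −6 | Gap |
|---|---|---|---|
| 100% | 247 | 254 | 7 |
| 75% | 253 | 257 | 4 |
| 50% | 258 | 261 | 3 |
| 25% | 264 | 265 | 1 |
| 0% | 269 | 269 | 0 |

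**4. How often would the two disagree?** With all PWID and a true rate of 88.7%, P(X ≥ 247) = 80.4% and P(X ≥ 254) = 32.8%. The difference is 47.6%, so about 48% of all trials would pass while the interval still includes −6. At shares of 75%, 50%, 25% and 0% this is 26%, 14%, 2% and 0%.

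**5. What if the test is read as a claim about the true chronic rate?** Averaged over redrawn controls of 62, with a true chronic PWID rate of 88.7% and a true 6-point loss, an all-PWID trial passes 15.0% of the time. This is not the error rate given the 55/62 already observed. Given that control, the chance of passing at a true 6-point loss is 0.02%, 2.2%, 30% or 76% if the true chronic PWID rate is 85%, 88.7%, 92% or 94.4%. The figure follows the assumed rate, which the documents cannot supply. It also concerns a claim that the plan's test does not make.

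**The case for a change.** The strongest case for the addition is that the objective and the margin are worded as loss relative to chronic HCV, that the display costs one paragraph and one table row, and that fixing its method in advance is better than choosing it after results. Three parts of this stand. No analysis carries the control's sampling error. The all-PWID gap of 7 responders is not trivial. A pass does not by itself prove less than a 6-point loss against the true chronic rate.

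The rest does not make the plan deficient.

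- The same section that states the objective also states the rule by which it is judged, and the choice of a threshold is explained, with the counts printed.
- Because those counts are fixed and the display would decide nothing, it can be produced at reporting without changing the SAP. The PWID-stratum Wilson intervals in SAP 9.6 already let a reader set like against like.
- The interval has drawbacks of its own. It would carry binomial error only, not differences between studies or between acute and chronic disease. It could easily be misread as a failed non-inferiority test, and further enrolment could not remove the imprecision of a control of 62.
- Much of the imprecision concerns non-virologic loss: only 1 of the 7 historical PWID non-responders (62 − 55) was a virologic failure. For the key secondary analysis with all PWID, the pass mark and the count excluding −6 differ by one subject (244 and 245 of 255).

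**Conclusion.** The concern does not hold. The plan tests superiority to a prespecified threshold, says so, and achieves the stated operating characteristics (all PWID: exact level 2.2%, power 80.4%). Following it as written gives a sound conclusion about that threshold. The missing item is an optional descriptive display that would leave the test, the threshold and the testing sequence unchanged. Whether to show it is a reporting preference with a real trade-off.

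This rests on two conditions. The historical rates are taken as constants, as the plan defines them. A pass is reported as SVR12 above the threshold, not as a demonstrated bound on the loss against the true chronic rate. The practical weight of the point depends on the enrolled PWID share: 7 responders between the two criteria if all are PWID, 1 at a quarter, none if there are no PWID.

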7 STATISTICAL METHODS & DETERMINATION OF SAMPLE SIZE

7.1 Statistical and Analytical Plans

The statistical methods provided in this protocol will be focused on primary and secondary analyses. Complete and specific details of the statistical analysis will be described in the SAP.

SAS (SAS Institute, Inc., Cary, NC) for the UNIX operating system will be used for all analyses. All confidence intervals will be 2-sided with an alpha level of 0.05.

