## 12.0 Overall Type-I Error Control

In order to control the family-wise Type-I error rate, a fixed-sequence testing procedure will be used for the primary and key secondary efficacy analyses of SVR12 listed below. The fixed-sequence testing procedure will utilize the sequence of the primary analysis followed by the key secondary analysis.

The multiplicity-controlled efficacy analyses will be performed sequentially in the following order:

1. Primary: Superiority of the SVR12 rate of 8-week treatment with GLE/PIB for subjects in the ITT population to the efficacy threshold. If superiority is demonstrated, then proceed to the key secondary efficacy analysis. If superiority is not demonstrated in the primary analysis, then stop the testing procedure (i.e., do not perform the key secondary analysis).

2. Key Secondary: Superiority of the SVR12 rate of 8-week treatment with GLE/PIB for subjects in the mITT-VF population to the efficacy threshold. If superiority is demonstrated, then declare superiority for both the mITT-VF and ITT populations. If not, then declare that superiority was demonstrated only for the ITT population.

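### The >95% power stated for the key secondary test in the all-PWID case ignores the gatekeeper; under the planned fixed sequence it is about 80%

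*Protocol*

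**What the plan says.** Protocol 7.8 sizes the trial under two bounding cases, all PWID and all non-PWID. For the primary (ITT) test in the all-PWID case it states that "283 subjects will provide 80% power to show that an 88.7" percent SVR12 rate exceeds the 82.7% threshold. For the key secondary (mITT-VF) test in the same case, with about 10% of ITT subjects excluded, it states that "a total of 255 subjects will provide greater than 95% power to show that a 98.2" percent rate exceeds 92.2%. In the all-non-PWID case both tests are given more than 95% power. SAP 2.5 gives the same figures.

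The two tests are hierarchical. Protocol 7.4 says: "The key secondary hypothesis will be tested only if the primary efficacy hypothesis is demonstrated". Protocol 7.7 adds: "If superiority is not demonstrated in the primary analysis, then stop the testing procedure (i.e., do not perform the key secondary analysis". SAP 9.4.2 and 12.0 carry the same rule.

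Protocol 4.2 describes the target population in these words: "Given that the acute HCV population is comprised primarily of PWID patients". Neither document gives an expected PWID share for this trial.

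**The concern.** Superiority in the mITT-VF population can be declared only by passing through the primary test. Its power under the plan therefore cannot exceed the primary's, which Protocol 7.8 puts at 80% in the all-PWID case. The next paragraph of the same section nevertheless gives more than 95% for the key secondary claim in that case, without saying that the gate has been left out.

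A reader of the key secondary paragraph alone would think that claim 15 to 20 points safer than the procedure makes it. It is one of only two claims under multiplicity control, so what is at stake is an accurate statement of the chance of reaching it, and how a sequence that stops early would later be read.

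**Working it through.** **Inputs.** Protocol 7.1 sets the level: "All confidence intervals will be 2-sided with an alpha level of 0.05". Protocol 7.4 sets the success rule for both tests: "the lower bound of the 2-sided 95% confidence interval (using Wilson's score method") must exceed the threshold. The sizes (283 and 255), assumed true rates (88.7% and 98.2% for PWID, 97.8% and 98.8% for non-PWID) and thresholds (82.7%, 92.2%, 91.8%, 92.8%) come from Protocol 7.8.

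**Responders needed.** The Wilson lower bound exceeds p0 exactly when x > n·p0 + 1.96·√(n·p0·(1−p0)).

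- Primary, all PWID: 283 × 0.827 + 1.96 × √(283 × 0.827 × 0.173) = 234.04 + 12.47 = 246.51, so at least 247.
- Key secondary, all PWID: 255 × 0.922 + 1.96 × √(255 × 0.922 × 0.078) = 235.11 + 8.39 = 243.50, so at least 244.

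The same formula gives 269 of 283 and 245 of 255 in the all-non-PWID case.

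**Stand-alone power, P(X ≥ x_min) with X binomial at the assumed rate.**

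| Case | Test | Needed | Power | Plan states |
|---|---|---|---|---|
| All PWID | Primary | 247/283 | 80.4% | 80% |
| All PWID | Key secondary | 244/255 | 99.7% | >95% |
| All non-PWID | Primary | 269/283 | 99.8% | >95% |
| All non-PWID | Key secondary | 245/255 | >99.9% | >95% |

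All four stated figures reproduce, each as the power of a single test.

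**Power under the sequence, without a model.** Whatever the dependence between the two tests, the probability that both succeed lies between P + S − 1 and min(P, S). In the all-PWID case this is 80.40 + 99.75 − 100 = 80.15% to 80.40%.

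**Power under the sequence, exact.** Each ITT subject has one of three outcomes: SVR12, virologic failure, or other non-response (excluded from mITT-VF). For PWID, SVR12 has probability 0.887. An mITT-VF rate of 98.2% then requires a virologic failure probability of 0.887 × 0.018/0.982 = 0.0163. The mITT-VF share is 0.887 + 0.0163 = 0.903, that is 9.7% excluded, in line with the plan's 10%. Summing over all outcomes of 283 subjects, with the mITT-VF size left random:

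- All PWID: primary 80.40%, both 80.33%. Power of the key secondary given a primary success is 80.33/80.40 = 99.9%.
- All non-PWID: both 99.8%.

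**Mixed populations.** The PWID shares here are assumptions, because the documents give none. Each stratum keeps its historical rates, and both thresholds are recomputed from the PWID shares as Protocol 7.8 prescribes.

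| PWID of 283 | Share | Primary | Both |
|---|---|---|---|
| 255 | 90% | 83.9% | 83.9% |
| 212 | 75% | 85.1% | 85.1% |
| 142 | 50% | 93.2% | 93.2% |
| 99 | 35% | 94.8% | 94.8% |
| 71 | 25% | 97.1% | 97.1% |

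Over all PWID majorities (142 to 283 subjects) the power for both runs from 78.2% to 93.2%. It exceeds 95% at every mix up to 98 PWID (34.6%) and at none above 116 (41%); between these it moves above and below 95% because the binomial is discrete. At every mix it is within 0.1 point of the primary power.

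**Sensitivity.** If exactly 10% are excluded and 98.2% holds in mITT-VF, the ITT rate is 0.9 × 0.982 = 88.4% and the power for both, all PWID, is 75.2%. With the historical PWID split given in Protocol 4.2 (55/62 SVR12, 1/62 virologic failure, hence 6/62 other) it is 80.5%.

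**The case against.** The strongest reply is that the figure is correct for what it describes: one comparison, with its own size, rate, threshold and interval. It is also correct as power given a primary success, which is the only situation in which the test is run. The 80% for the primary stands in the preceding paragraph and the gate is stated plainly, so the ceiling can be inferred without calculation. Reporting power test by test and describing the hierarchy separately is a coherent convention. Nothing in the design or analysis depends on the figure, and all-PWID is only a bounding case.

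Much of this stands. There is no arithmetic error, multiplicity control is intact, and nearly all of the gap is the primary's chance of failure, which is disclosed. What does not stand is that the label can be left out. The text speaks of power to show superiority, and superiority can be declared only through the sequence. Neither document calls the figure stand-alone or conditional. Nor is the gap confined to the corner case: at every PWID majority the power under the sequence is below 95%.

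**Conclusion.** The point holds and is of modest importance. In the all-PWID case the stated >95% is stand-alone power. Under the plan's own fixed sequence the key secondary claim has about 80% power (80.3% exact; 80.1% to 80.4% under any dependence between the tests). The all-non-PWID statement is right under the sequence too (99.8%).

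The all-PWID result needs only the plan's own rates, sizes and thresholds. The range for PWID majorities also rests on assumed PWID shares and on the historical stratum rates being true in this trial. What needs correcting is how one power figure is reported; the design itself is not in question.

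**What to change.** In Protocol 7.8 and SAP 2.5, label the all-PWID key secondary figure as stand-alone power that ignores the gatekeeper, and add one sentence: *Under the fixed-sequence procedure, the power to show both the primary and the key secondary claim is about 80% if all subjects are PWID and greater than 95% if all are non-PWID.*

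The cost is one label and one sentence in each document. No subjects are added, and the thresholds, test order and analysis stay as they are. The only drawback is a less favourable stated figure.
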